### 9.1.2 Serious Adverse Event

An SAE is defined as any adverse experience occurring at any dose of study medication that occurs between the time the patient signs the informed consent form through the end-of-study that results in any of the following outcomes:

- Death
- Life-threatening situation (patient is at immediate risk of death)
- In-patient hospitalization or prolongation of existing hospitalization for a clinically relevant reason (note that this excludes “social” hospitalization for nonmedical causes such as lack of transportation to home)
- Persistent or significant disability/incapacity
- Congenital anomaly/birth defect in the offspring of a patient who received study drug
- Important medical events that may not result in death, be life-threatening, or require hospitalization may be considered serious when, based upon appropriate medical judgment, they may jeopardize the patient or patient may require medical or surgical intervention to prevent one of the outcomes listed in this definition. Examples may include, but are not limited to:
  - Intensive treatment in an emergency room or at home for allergic bronchospasm
  - Blood dyscrasias that do not result in hospitalization
  - Seizures that do not result in hospitalization

A hospitalization meeting the regulatory definition for “serious” is any in-patient hospital admission that includes a minimum of an overnight stay in a health care facility.

---

Worsening and/or flares of EPI disease activity should be recorded in the appropriate EPI CRF. However, if disease worsening meets any of the criteria for an SAE, then it must be recorded on the SAE form and reported to the Sponsor or designee within 24 hours of becoming aware of the event.

### 9.1.3 “Serious” vs “Severe” Adverse Event

To avoid confusion or misunderstanding over the difference between the terms “serious” and “severe,” which are not synonymous, the following note of clarification is provided (excerpted from International Council for Harmonisation [ICH] E2A):

*The term “severe” is often used to describe the intensity (severity) of a specific event (as in mild, moderate, or severe myocardial infarction); the event itself, however, may be of relatively minor medical significance (such as severe headache). This is not the same as “serious,” which is based on patient/event outcome or action criteria usually associated with events that pose a threat to a patient’s life or functioning. Seriousness (not severity) serves as a guide for defining regulatory reporting obligations.*

### 9.1.4 SAE Definition Clarifications

- Death is an outcome of an AE, and not an AE in itself.
- All deaths during study through the end-of-study, regardless of cause or relationship, must be reported.
- “Occurring at any dose” does not imply that the patient is actively receiving study drug at the time of the event.
- “Life-threatening” means that the patient was at immediate risk of death from the event as it occurred. This does not include an event that might have led to death, had it occurred with greater severity.
- Complications that occur during hospitalizations are AEs. If an AE prolongs hospitalization, it is an SAE.
- “In-patient hospitalization” means the patient has been formally admitted to a hospital for medical reasons, for any length of time, excepting situations where an untoward medical occurrence has not occurred (eg, hospitalization for elective surgery, social, or convenience admissions). Hospitalization may or may not be overnight. It does not include presentation and care within an emergency department (although an emergency department visit may define a medically important event, which is also considered an SAE).

- If any AE worsens during the study and eventually meets the criteria for an SAE the AE should be recorded as a new SAE.

## 9.2 Reporting Procedures for All Adverse Events

AEs will be recorded in the CRF for all patients from the time the patient signs the informed consent form through the end of the study or patient withdrawal.

The Investigator is responsible for ensuring that all AEs (as defined in [Section 9.1](#) and as further specified below) observed by the Investigator or reported by patients are collected and recorded in the patients' medical records, in the CRF, and as an SAE in the electronic data capture system. These AEs will include the following:

1. All SAEs (as defined in [Section 9.1.2](#)) that occur.
2. All nonserious AEs (as defined in [Section 9.1.1](#)) that occur.

The following AE attributes must be assigned by the Investigator:

- AE diagnosis or syndrome(s) (if known, signs or symptoms if not known);
- event description (with detail appropriate to the event);
- dates of onset and resolution; severity; assessment of relatedness to study drug; and
- action taken with study medication.

The Investigator may be asked to provide follow-up information, discharge summaries, and extracts from medical records or CRFs.

It will be left to the Investigator's clinical judgment to determine whether the relatedness of an AE, and of sufficient severity to require the patient's removal from treatment or from the study. A patient may also voluntarily withdraw from treatment because of what he or she perceives as an intolerable AE. If either of these situations arises, the patient should be strongly encouraged to complete the End-of-Therapy assessments and be under medical supervision until symptoms cease or the condition becomes stable.

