#### 7.3.4 Removal of Patients from the Study

A patient may be withdrawn from the study at any time for any of the following reasons:

- Loss to follow-up
- Withdrawal of consent, for any reason, at any time
- Major protocol deviations that could compromise the interpretation of the results
- Occurrence of an immunoallergic reaction
- Occurrence of an adverse reaction (ie, an SAE related to IMP) that justifies the discontinuation of the IMP
- Pregnancy

The date of withdrawal and the reason for withdrawal must be fully documented in the case report form (CRF) and a short narrative description should be added in the patient's medical records.

If at the time of withdrawal, the patient has received the investigational study product (partially or totally), study staff should encourage the patient to attend the Early Withdrawal

---

Visit for follow-up safety investigations. These patients will be included in the ITT efficacy analysis and safety analysis.

If the reason for discontinuation is an AE, then the Investigator will seek to obtain follow-up information and to document the event until its resolution or stabilization. In any case, the Investigator will take all necessary measures to ensure the patient's safety and ensure the patient is treated in accordance with local standard of care.

If a patient is lost to follow-up, then the Investigator should make every effort to obtain maximum information on the reasons for the nonattendance to the visit and on the patient's state of health. All attempts will be documented in the patient's medical records.

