## 8.3 Second Treatment Period (Visits 7 [T], 8 [T] and 9)

The second treatment period will begin once patients have passed their second blue dye marker at the end of V6, and the stool sample collection is complete. As soon as this has occurred, patients will crossover to their new treatment (either MS1819-SD or patient's prestudy porcine PERT).

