8.3 Adverse Events

Adverse events will be coded using the Medical Dictionary for Regulatory Activities (MedDRA) Version 21.1 to identify the system organ class and preferred term.

Adverse events that occur or are reported to worsen in severity on or after date of first dose of study treatment in period 1 will be considered to be TEAEs.

TEAEs will be categorized as occurring in either study period 1 or study period 2 according to the following rules:

- Adverse events that occur or are reported to worsen in severity on or after date and time of start of period 1 study treatment and on or before date and time of end of period 1 study treatment will be attributed to study period 1. Adverse events that occur or are reported to worsen in severity on the start date of period 1 study treatment that do not have a time associated with the event will be attributed to study period 1.
- Adverse events that occur or are reported to worsen in severity after the end date of period 1 study treatment and on or before the date of end of period 2 study treatment will be attributed to study period 2. Adverse events that occur or are reported to worsen in severity on the date of end of period 2 study treatment that do not have a time associated with the event will be attributed to study period 2.

- Adverse events that occur on the crossover date between study period 1 and study period 2 that do not have a time associated with the event will be attributed to study period 1.
- Adverse events that occur in both study period 1 and study period 2 will be attributed to both study periods.

TEAEs that occurred after the subject's last study period will be classified as follow-up TEAEs. If a subject entered both the first and second study periods, any event occurring after the end date of the second study period will be considered a follow-up TEAE. If a subject discontinued prior to the start of the second study period, any event occurring after the end date of the first study period will be considered a follow-up TEAE.

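### Protocol 9.2 requires only AE dates, and the SAP 8.3 period rules can place an untimed crossover-day event under the wrong treatment and leave a timed one in neither period

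*Protocol*

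**What the plan says.** **Collection.** Protocol 9.2 gives the attributes the investigator must assign to each adverse event. The only timing item is in "dates of onset and resolution; severity; assessment of relatedness to study drug; and".

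**Attribution.** SAP 8.3 assigns treatment-emergent events to periods by three rules that matter here:
- Period 1 takes events "on or before date and time of end of period 1 study treatment will be attributed to study period 1".
- Period 2 takes events "after the end date of period 1 study treatment and on or before the date of end of period 2 study treatment".
- "Adverse events that occur on the crossover date between study period 1 and study period 2 that do not have a time associated" with them go to Period 1.

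**Tabulation.** SAP 8.1 then summarises safety by actual treatment regardless of period, so the period assignment decides the treatment column.

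**The switch.** Protocol 7.1 and SAP 2.2 state that there is no washout. Protocol 8.3 ties the switch to passage of the second dye marker at the end of Visit 6: "As soon as this has occurred, patients will crossover to their new treatment".

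**The concern.** The crossover date is the one day on which a patient can take both treatments, and only a clock time can separate them. The protocol does not require that time, and the SAP default for its absence is the treatment just finished. In a PERT-first patient that day may also be the first day ever on MS1819, so an acute reaction to the new enzyme could appear in the comparator's column.

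Safety is a primary objective (Protocol 6.1), this is the first study of MS1819-SD in cystic fibrosis (Protocol 5.8), and Protocol 7.3.4 names "Occurrence of an immunoallergic reaction" as a reason for withdrawal. First-dose reactions are the events most exposed to the rule. The same default works the other way in MS1819-first patients, where an untimed event after the return to PERT is counted under MS1819.

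**Working it through.** The plan gives no figure on this point to reproduce. The check sets the rules against the possible cases and then sizes the effect.

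**Cases on the crossover date.** The SAP does not define that date. I take it as the day on which Period 1 treatment ends and Period 2 treatment starts.

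| Onset relative to the switch | Time recorded? | Where SAP 8.3 puts it | Correct? |
|---|---|---|---|
| Before | Yes | Period 1 | Yes |
| Before | No | Period 1 (default) | Yes |
| After first Period 2 dose | No | Period 1 (default) | No |
| After first Period 2 dose | Yes | Neither: too late for Period 1, and not after the Period 1 end date | No |

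The last row shows that recording times is not enough by itself. A post-switch event with a time fails the Period 1 test on time and the Period 2 test on date. It remains treatment-emergent but has no period, and hence no treatment column.

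**Comparison with the SAP's other rules.** An untimed event on the Period 1 start date goes to Period 1, the treatment just started (SAP 8.3). An event with a missing start day that could belong to either period can have its start imputed to both treatment starts (SAP 8.1). Missing relatedness or severity is taken at its maximum (SAP 8.3). Only the untimed crossover-date event is assigned to the earlier treatment alone.

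**Effect of one misplaced patient.** Inputs: 38 enrolled or 30 completers (Protocol 10.2), with the safety population as denominator for every percentage (SAP 8.3). If the event is that patient's only one in the row, the correct column loses 1/n and the other gains 1/n, so the difference moves by 2/n:
- n = 38: 100/38 = 2.6 points per column, 200/38 = 5.3 points in the difference.
- n = 30: 100/30 = 3.3 points per column, 200/30 = 6.7 points in the difference.

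**Share of events exposed.** One day of a 21-day period is 1/21 = 4.8%. Evenly spread onsets are therefore little affected; events clustered at the first dose are the exposed group.

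**Illustration for first-day MS1819 reactions.** These inputs are assumptions: true rate r = 10% on MS1819 and 0% on PERT, equal sequences of 19, and a share p of the PERT-first reactions falling on the crossover date without a time. The table shows MS1819 at r(1 − p/2) and PERT at r·p/2, a difference of r(1 − p).

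| p | MS1819 shown | PERT shown | Difference | Share of reactions moved (p/2) |
|---|---|---|---|---|
| 0.25 | 8.75% | 1.25% | 7.5 points | 12.5% |
| 0.50 | 7.5% | 2.5% | 5.0 points | 25% |
| 0.75 | 6.25% | 3.75% | 2.5 points | 37.5% |
| 1.00 | 5% | 5% | 0 points | 50% |

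The documents give no value for p.

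**Are untimed onsets plausible?** The SAP provides for them. On nominal days, admission is Day 17, the second marker is given on the fourth day of confinement (Day 20), and the stay ends by about Day 24. The next scheduled contact about adverse events is the Day 29 call (Visit 7), which is 29 − 24 = 5 to 29 − 20 = 9 days later. An exact onset time would then rest on recall.

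**The case against.** Protocol 9.2 is a list of required attributes and does not forbid recording a time. SAP 8.3 uses date and time and confines its default to events lacking a time, so it expects some events to have one. The CRF is not among the documents and may already hold a time field. A reader might infer that only dates are collected; the documents do not support that. What stands is that no time is required.

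A reader might also infer that about half of first-day MS1819 reactions land under PERT and that the safety tables are therefore wrong. That is only the p = 1 case. It needs every such event in PERT-first patients to be untimed and to fall on the crossover date. MS1819 is taken with food and follows the second marker stool, so a late stool could push the first dose to the next day.

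Nor does the rule simply favour MS1819, since it errs in both directions. The errors differ in consequence, because a lost acute signal matters more for the new product than for each patient's established therapy.

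Several features soften the effect, and they stand. Relatedness is scored separately for each treatment and tabulated. All events are listed. Events occurring in both periods are attributed to both, so a reaction that continues may also reach the MS1819 column. The DSMB chair receives serious event reports in real time (Protocol 10.6). Safety is descriptive, so no test or decision rule depends on the split. These features help a reader find a misplaced event, but they do not put it in the right column.

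On the timed events that fit neither rule, a programmer would probably read the Period 2 rule as if it included the time. The text does not say so.

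**Conclusion.** The point holds as a conditional misclassification in both sequences, together with a drafting gap for timed events. The misclassification needs three things: an event on the crossover date, onset after a first Period 2 dose taken that day, and no recorded time. The gap needs Period 1 treatment to end on that same date.

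Each misplaced patient shifts the displayed difference by 5.3 points (n = 38) or 6.7 points (n = 30), if it is that patient's only such event. For evenly spread onsets about 4.8% of Period 2 events are exposed. How many patients would be affected cannot be derived from the documents.

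The effect is probably small overall, but it falls on first-dose reactions in a primary safety comparison and is cheap to remove. Assigning every untimed crossover-date event to MS1819 is a tempting remedy that I would not adopt. It assumes MS1819 is taken on that date in both sequences, which the documents do not establish, and it would charge some PERT events to MS1819.

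**What to change.** 1. **Protocol 9.2:** require the clock time of onset for any adverse event starting on the crossover date, in addition to the dates.
2. **SAP 8.3:** define Period 2 as starting at the date and time of the first Period 2 dose, and define the crossover date. SAP 8.2 already lists the date and time of first and last dose in each period, so no new dosing data are needed.
3. **SAP 8.3:** count crossover-date events that remain untimed in both periods, in line with the SAP 8.1 treatment of ambiguous partial dates. Alternatively, keep the present default and show the both-periods version as a sensitivity table.

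The cost is one time field, if the CRF does not already have it, and a few SAP sentences. The downside is that a few events will be counted under both treatments. For such an event the true column is right and the other is overstated by 1/n, so the error in the difference is 2.6 points (n = 38) or 3.3 points (n = 30), half of what a wrong single assignment gives. If event collection has already finished, items 2 and 3 can still be made before the analysis.

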## 9.3 Grading of Adverse Events

The Investigator will be asked to provide an assessment of the severity of the AE using the categories noted below. This assessment is subjective, and the Investigator should use medical judgment to compare the reported AE to similar events observed in clinical practice. It is important to recognize that severity is not equivalent to event seriousness.

**Grade 1 (Mild):** usually transient; requires no special treatment and does not generally interfere with the patient's daily activities.

**Grade 2 (Moderate):** produces a mild to moderate level of inconvenience to the patient and may interfere with daily activities. These events are usually ameliorated by simple therapeutic measures.

**Grade 3 (Severe):** significantly interrupts daily activity and requires systemic drug therapy or other medical treatment.

#### **9.4 Relationship to Study Drug**

For each reported AE, the Investigator must make an assessment of the relationship of the event to the study drug using the following scale:

**Unrelated:** The event is definitely not or unlikely associated with study drug administration and is judged because of causes other than the study drug.

**Related:** Events considered to be related are those that follow a reasonable temporal sequence from administration of the study drug, that are not easily explained by another cause such as known characteristics of the patient's clinical state or other treatment or confirmed by improvement on stopping or slowing administration of the study agent (de-challenge), if applicable.

#### **9.5 Serious Adverse Event Reporting Procedures**

Serious adverse events will be recorded from the time the patient signs the informed consent form through the end of study. AEs will be followed until the event resolves or stabilizes, or until the end of study for that patient.

If the AE is an SAE and is assessed as "related to study drug", it must be followed until either the event is considered stable or resolved.

Any SAE assessed as "unrelated to study drug" will be followed as clinically indicated until its resolution or, if not resolving, until considered stable or until the final study visit for that patient whichever comes first.

All SAEs that occur must be reported within 24 hours of discovery or notification of the event. Initial SAE information and all amendments or additions must be recorded as an SAE in the electronic data capture system and sent to the Sponsor or designee.

---

If a patient is permanently withdrawn from the study because of an SAE, then this information must be captured as an SAE in the initial or follow-up electronic data capture record as well as the End-of-Therapy CRF.

The Investigator should notify the appropriate IEC/IRB of SAEs occurring at the site and other SAE reports received from AzurRx, in accordance with local procedures and statutes.

AzurRx will ensure that applicable regulatory authorities receive all relevant information on an SAE, in accordance with regulatory requirements. Results of AzurRx's investigation of other safety information shall be submitted, as required.

## **9.6 Pregnancy Reporting Procedures**

Patients must be instructed to inform the Investigator immediately if they or their partners become pregnant after the patient has received their first dose of investigational product during the study. The following actions should be taken in the event of a confirmed pregnancy:

1. For female patients, study drug should be discontinued immediately.
2. The pregnancy should be reported to the Safety Group within 24 hours of notification using the applicable Pregnancy Report Form.
3. The Investigator should counsel the patient regarding the possible effects of previous study drug exposure on the fetus and the need to inform the study site of the outcome of the pregnancy.
4. The patient or the patient's pregnant partner must be monitored until the immediate postnatal period or until termination of the pregnancy. The outcome should be reported to the Medical Monitor using the Pregnancy Outcome Form.

Pregnancy is not an AE in and of itself. However, any pregnancy complications or elective terminations of a pregnancy for medical reasons will be recorded as an AE or SAE. A spontaneous abortion is always considered an SAE and will be reported as described in the AE and SAE sections (Section 9.2 and Section 9.5). Furthermore, any SAE occurring as an adverse pregnancy outcome poststudy must be reported to the Medical Monitor.

## **9.7 Hepatic Monitoring**

The following guidelines are provided for the management of serum transaminase elevations in patients with new, clinically-meaningful increases in liver function tests occurring during the study. All cases of new (ie, since screening) elevations in ALT or AST  $\geq 3$  times ULN or any questions concerning the management of a patient with elevated serum transaminases should be discussed with the study Medical Monitor.

---

Patients who experience a new (ie, since screening) elevation in ALT or AST level to  $\geq 3 \times$  ULN OR total bilirubin  $\geq 1.5 \times$  ULN will have hepatic monitoring until one of the following occurs:

- Withdrawal from study if elevation in ALT or AST level to  $\geq 3 \times$  ULN is associated with a rise in total serum bilirubin to  $\geq 2 \times$  ULN (without laboratory findings of cholestasis [elevated serum alkaline phosphatase  $\geq 2 \times$  ULN])
- Withdrawal from study if elevation in ALT or AST level to  $\geq 5 \times$  ULN is associated with new or exacerbated gastrointestinal (GI) symptoms (ie, nausea, vomiting, right upper quadrant pain, and/or jaundice) and other causes are not evident
- Withdrawal from the study if elevation in ALT or AST is  $\geq 10 \times$  ULN regardless of serum bilirubin level

Causes of acute elevation of transaminases should be considered and ruled out (e.g., viral hepatitis, concomitant medications).

Patients discontinued from study drug administration should resume porcine PERT therapy according to physician prescription.

